5.2 Independent of the primary outcome

Change from baseline in:

- Blood pressure. A test for interaction by race (White, Black/African American vs. Other) will be done.^{13,14}
- Cardiovascular risk factors:
 - Cholesterol profile
 - Total cholesterol
 - HDL
 - LDL
 - Triglycerides
 - C-reactive protein
 - Urine albumin excretion
- ASCVD risk score (ACC/AHA) calculated using clinical and laboratory criteria.
- 25OHD

NOTE: For certain variables (e.g., cardiovascular risk factors, 25OHD), the analyses will take place in a sub-cohort with available laboratory data at the BAS, M12 and M24 visit.

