4.3.7 Measurements of Other Exposures

Vitamin D status. Plasma 25OHD concentration will be measured as a proxy for vitamin D status at baseline and yearly during follow-up to assess the efficacy of the intervention in the active arm at improving vitamin D status and to evaluate for heterogeneity of treatment effect by achieved 25OHD concentration. Measurement of 25OHD will not be done in real-time (see 7.6). *Self-reported vitamin D intake* will be estimated from a validated self-administered semi-quantitative food frequency questionnaire administered at baseline, month 12 and month 36 in participants free of diabetes.^{18,234-237}

Calcium status. There are no widely accepted measures of adequacy of calcium status. Calcium intake will be used as proxy of calcium adequacy at baseline and during the intervention. *Self-reported calcium intake* will be estimated from a validated food frequency questionnaire administered at baseline, month 12 and month 36 in participants free of diabetes.¹⁸

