9.2 Secondary Endpoints (Outcomes) & Subgroup Analyses

The secondary outcomes were selected based on their importance to the underlying hypothesis of a potential link between vitamin D and type 2 diabetes (e.g. identify mechanisms that explain the effect of vitamin D supplementation on the primary outcome). Additional secondary outcomes that are not directly relevant to type 2 diabetes may be included, depending on budget and burden consideration, to increase our understanding of vitamin D physiology and its relevance to other outcomes, thereby maximizing the yield of the study. Secondary outcomes will be assessed in the entire cohort or in subsets of the study population, depending on statistical power needs, feasibility and availability of funding.

- Variability of response to vitamin D supplementation in subgroups defined by baseline characteristics: (1) race and ethnicity (as proxies for skin pigmentation);¹⁸⁶ (2) BMI; (3) waist circumference;^{187,188} (4) age; (5) geographic location (proxy for sun exposure); (6) 25OHD concentration.
- Variability of response to vitamin D supplementation by adherence based on pills counts and by achieved 25OH concentration.
- Effect of vitamin D supplementation on HbA1c, FPG and 2hPG as continuous variables.
- Effect of vitamin D supplementation on insulin resistance and beta cell secretion (indices derived from the OGTT).
- Effect of vitamin D supplementation on plasma 25OHD concentration and identification of phenotypic, including seasonal and geographic, characteristics associated with variability on achieved plasma 25OHD concentration.
- Effect of vitamin D supplementation on blood pressure.
- Safety and tolerability of vitamin D supplementation.

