3.2.2 Secondary outcomes – independent of the primary outcome: continuous variables

- Blood pressure (baseline and semi-annually)
- Cardiovascular risk factors: cholesterol profile, C-reactive protein, urine albumin excretion (baseline, M12 and M24)
- Atherosclerotic Cardiovascular Disease (ASCVD) ACC/AHA composite risk score (baseline, M12, M24)

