3.3 Explanatory outcome: continuous variable

- 25OHD concentration (baseline, M12 and M24)

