5 SECONDARY ANALYSES

Effect of vitamin D supplementation on secondary outcomes (**as continuous variables**) will be based on a linear mixed model and account for within subject correlation in repeated measurements over time. The overall mean difference between vitamin D and placebo groups for these analyses will be tested using the nominal 0.05 type 1 error rate *without adjustment for multiple comparisons*.^{11,12}

Some of these analyses (e.g., insulin secretion, cardiovascular risk factors) will not be presented in the main manuscript but in separate publications.

5.1 Related to the primary outcome (i.e., diabetes).

Change from baseline in:

- HbA1c, FPG and 2hPG
- Insulin secretion, sensitivity and disposition index. (indices derived from the OGTT).

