7 MISSING DATA

Missing data are inevitable in clinical research. Every effort has been made to minimize missing data in D2d. The primary analysis will assume that censoring for time-to-event variables is non-informative. However, we will perform sensitivity analyses to assess the degree to which the results are sensitive to the validity of the assumptions of non-informative censoring or non-informative missingness. For the secondary analyses using linear mixed effects models over time, results will be valid unless data are not missing at random.

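### The SAP 5.2 NOTE, read plainly, limits the 25OHD and cardiovascular risk factor analyses to participants with data at baseline, M12 and M24, which removes the partial records that the mixed model needs

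*SAP*

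**What the plan says.** SAP 5 states that continuous secondary outcomes "will be based on a linear mixed model and account for within subject correlation in repeated measurements over time". SAP 7 then says of these models that "results will be valid unless data are not missing at random".

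The NOTE at the end of SAP 5.2 gives a different population for certain variables, with cardiovascular risk factors and 25OHD as its examples: "the analyses will take place in a sub-cohort with available laboratory data at the BAS, M12 and M24 visit".

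The visit schedule for the same variables is already set elsewhere in the SAP. Section 3.2.2 lists "cholesterol profile, C-reactive protein, urine albumin excretion (baseline, M12 and M24") and gives the same three visits for the composite cardiovascular risk score. Section 3.3 lists "25OHD concentration (baseline, M12 and M24").

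The protocol is broader in two places. Section 4.3.7 states that "Plasma 25OHD concentration will be measured as a proxy for vitamin D status at baseline and yearly during follow-up". Section 9.2 allows that "Secondary outcomes will be assessed in the entire cohort or in subsets of the study population", depending on power, feasibility and funding.

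Neither document says how the sub-cohort is selected, how large it is, whether all three values are required, or whether membership is fixed by randomisation. No all-available-data analysis of these outcomes is specified alongside it.

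**The concern.** A linear mixed model handles data that are missing at random because participants with incomplete records stay in the likelihood: an observed M12 value informs the unobserved M24 value. If the analysis set holds only people with all three values, no incomplete records are left. Validity then needs a stronger condition, namely that being a completer is unrelated to post-baseline outcome, or related to it identically in both arms.

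For 25OHD that condition is open to question. If participants who stop attending also tend to stop taking pills, their 25OHD falls in the vitamin D arm, while the placebo arm has no corresponding effect. A completer analysis would then overstate the separation between arms. The matter counts because the SAP labels 25OHD the explanatory outcome and the protocol uses it as its biomarker of adherence (section 7.6). Measured separation will therefore shape how a null or positive primary result is read.

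**Working it through.** **Which reading of the NOTE.** SAP 3.2.2 and 3.3 already fix the assay visits at baseline, M12 and M24. If the NOTE only repeated that schedule, it would add nothing. What it adds is a statement about who is analysed, so the plain reading is a restriction to people with data at those visits.

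**Inputs.** Protocol 11.1: 2,382 randomised; loss of up to 5% per year, given as a hazard of 0.0513. Protocol synopsis: attrition of at most 15% over the study. Protocol 4.3.1.2: mean 25OHD of about 20 ng/mL at entry and 35 to 40 ng/mL on 4,000 IU/day. If placebo does not move (assumed), the between-arm difference is 15 to 20 ng/mL. The documents give no size for the sub-cohort and no rate of missed visits.

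**The plan's own figure.** −ln(0.95) = 0.0513, which matches the protocol's hazard.

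**Participants lost under a three-visit rule, from loss to follow-up alone.**
- Still on study at M12: 0.95 × 2,382 = 2,263.
- Still on study at M24: 0.95² × 2,382 = 0.9025 × 2,382 = 2,150.
- Off study by M24: (1 − 0.9025) × 2,382 = 0.0975 × 2,382 = 232.
- Left in year two, so could have baseline and M12 data: 0.95 × 0.05 × 2,382 = 113.
- Left in year one, so have no post-baseline value: 232 − 113 = 119.

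**Alternative loss rates.** For 15% over 4 years, 1 − 0.85^(2/4) = 0.078, or 186 lost by M24. Of these, (0.85^(1/4) − 0.85^(2/4)) × 2,382 = (0.9602 − 0.9220) × 2,382 = 91 could have an M12 value. For 15% over 3 years, 1 − 0.85^(2/3) = 0.1027, or 245 lost.

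**Upper-end effect on 25OHD separation.** Suppose completers separate by D and all 113 partial completers by zero, with equal loss in both arms.
- All-available-data estimate: D × 2,150/2,263 = 0.95 D.
- Ratio of completer to all-available-data estimate: 2,263/2,150 = 1.05.
- In ng/mL: 0.05 × 15 = 0.75 (about 0.8) and 0.05 × 20 = 1.0.

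**When bias arises.** An illustrative simulation used 400,000 participants per arm, a true effect of zero, SD 1, an assumed correlation of 0.6 between visits, and M24 missingness driven by the observed M12 change.

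| Missing at M24 | Dropout unrelated to outcome, or related identically by arm | Dropout related differently by arm: completer bias |
|---|---|---|
| 5% | negligible | 0.02 to 0.06 SD over both visits |
| 10% | negligible | 0.06 to 0.12 SD at M12; 0.03 to 0.06 SD at M24 |
| 20% | negligible | 0.06 to 0.23 SD over both visits |

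In every scenario the likelihood estimate from all available data was within 0.005 SD of the full-data estimate. The mechanisms and missingness rates are assumptions, not figures from the documents.

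**The case against.** The strongest reply is that the NOTE does not say that all three values are required. Protocol 9.2 permits subsets, and protocol 3.2.3 places cholesterol, C-reactive protein and urine albumin in separately funded ancillary work. A sub-cohort picked for assay and measured at three visits is therefore a possible reading, and it fits SAP 5 and 7 better. This stands as a possibility and the documents do not settle it. It does not remove the point, because on that reading the selection rule is missing and nothing ties membership to baseline information.

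A reader might infer that the completer estimate of 25OHD separation is about 10% too high (1/0.9025 = 1.11). That figure compares completers with everyone randomised and assumes no separation in all 232 lost. The 119 with no post-baseline value are out of reach of any analysis proposed here, so the rule itself accounts for about 5% at most on these inputs. The 113 were also still attending at about M12 and may well have separated by then.

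A reader might also infer that the randomised comparison is broken. The documents do not support that. Treatment is double-masked (protocol 7.3.2), participants off pills stay in follow-up (7.5, 8.6), 25OHD sampling continues after diabetes (8.2.3), and section 8.5 separates leaving the study from stopping pills. These features limit differential loss but do not exclude it.

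SAP 7 does promise sensitivity analyses for informative missingness. It names none for these outcomes, and none that would bring partial records back.

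Finally, requiring any M12 or M24 value also selects on data after randomisation. That is true, but the selection is weaker, and it keeps the records that the model can use.

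**Conclusion.** The point holds in a limited form. On its plain reading, the NOTE selects on availability after randomisation and removes the partial records that the SAP's missing-data argument needs. On the alternative reading, it leaves the selection of the sub-cohort without a baseline rule. Either way the text should change.

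The size is modest. About 113 of 2,382 participants could have usable data discarded at the protocol's ceiling loss rate. The effect on 25OHD separation is about 5% even if those participants showed none, and would be unlikely to change a judgement on whether the arms separated. Missed visits would raise the count, as would event-driven close-out before the last enrollees reach M24. The protocol expects 586 events within four years under the null against a target of 508, so early close-out is possible. Loss from close-out is administrative, but the rule would still discard the M12 data of those participants.

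The scope is the secondary and explanatory laboratory outcomes covered by the NOTE, which lists its variables by example. The primary analysis, HbA1c, FPG and 2hPG are not named there.

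**What to change.** Reword the NOTE in SAP 5.2 as follows:
- Fit the linear mixed model to all randomised participants with a baseline value and any M12 or M24 value.
- If assays are limited, define the sub-cohort by random selection or by baseline information only, state the rule and the size, and keep every member who has a baseline value and any M12 or M24 value.
- Report the numbers with data by arm and visit, so that the remaining selection is visible.
- Keep the analysis of participants with all three values as a sensitivity analysis.

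The cost is a few sentences in the SAP and possibly some extra assays on stored samples from participants with partial follow-up.

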6 SAFETY ANALYSES

The safety analyses will examine the effect of vitamin D supplementation on the following safety outcomes.

- Hypercalcemia
- Hypercalciuria
- Nephrolithiasis

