3. HYPOTHESES AND SPECIFIC AIMS

3.1 Study Objectives

The *objectives* of the D2d study are to evaluate the safety of oral daily vitamin D supplementation and its effect on the time to onset of clinical diabetes in participants with pre-diabetes (at risk for type 2 diabetes).

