24. Any other unstable active medical condition (including but not limited to liver disease, wasting illness, AIDS, tuberculosis, oxygen-dependent chronic obstructive pulmonary disease, organ transplant, Cushing's syndrome) that in the opinion of the site investigators would impede competence or adherence with study procedures or increase risk. [Safety, adherence, plasma 25OHD may decrease as an acute-phase response^{254,255}] Such conditions will be assessed based on self-report and/or review of medical records (if available).
25. Uncontrolled hypertension (systolic blood pressure > 160 mm Hg or diastolic blood pressure > 100 mm Hg). [Safety]
26. Poor venous access. [Safety]

Laboratory Evaluation

27. Serum liver transaminase (ALT or AST) higher than 3 times the normal range for the clinical site's laboratory [Safety]
28. Anemia (hematocrit < 32 for women, < 36 for men), whole blood transfusion (within 6 months of screening) or chronic requirement, whole blood donation (within 3 months of screening) or other condition (hemolysis, hemoglobinopathy) rendering HbA1c results unreliable as indicator of chronic glycemia. [Interference with outcome assessment] Participants who donate platelets are

not excluded. Whole blood transfusion or donation does *not* exclude participant, but screening and study visits need to be timed appropriately.

29. Low platelet count (< 50,000). [Safety for blood draws]
30. Chronic kidney disease, defined as estimated glomerular filtration rate [GFR] < 50 mL/min, from creatinine measured at the clinical site's laboratory and GFR calculated centrally. [Vitamin D homeostasis changes as GFR declines. These changes start when GFR falls around 40-60 mL/min per 1.73 m².^{256,257} The planning committee selected 50 mL/min as the exclusion cutoff to ensure that participants maintain GFR > 40 mL/min during the study] Please note: to prevent potential confusion, GFR units will be denoted as mL/min throughout the protocol and associated documents.
31. Hypercalcemia, defined as serum calcium concentration greater than or equal to the upper limit of normal, measured at the clinical site's laboratory. [Safety]
32. Hypercalciuria, defined as spot urine (morning void) calcium-creatinine ratio > 0.275.²⁵⁸ [Safety]

Other

33. Participation (within 30 days of screening) in another interventional research study. [Conflict, "contamination"]

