7.5 Modification of Study Intervention

If a participant is unable to tolerate the study pills due to safety concerns (i.e. symptom, sign or laboratory abnormality) or for any other reason, study pills will be temporarily held or permanently discontinued (depending on the reason). Specifically, study pills will be permanently discontinued for: hypercalcemia, nephrolithiasis, hypercalciuria and kidney dysfunction, per criteria defined in the Data and Safety Monitoring Plan (DSMP). Study pills will also be held or discontinued at participant’s request. Study pills may be temporarily held for an adverse event (that is unrelated to study pills) or for other reasons. Study pills will be held during pregnancy and lactation. Participants who permanently discontinue study pills will remain in the study and return for all remaining scheduled follow-up visits until study end, consistent with the intention-to-treat principle. The importance of remaining in the study, even if they stop taking the pills, will be emphasized to participants during the informed consent process and at every visit.

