8.2.2 Safety Laboratory Tests during the Study

To monitor safety, the following laboratory tests will be drawn and analyzed at each *site's clinical laboratory* at M03, M12, at yearly visits thereafter, and as needed to evaluate symptoms and/or physical signs. Results will be provided to participants and their health care provider(s).

- Serum calcium
- Serum creatinine and estimated creatinine clearance (GFR, calculated centrally)

To monitor safety, the following laboratory test will be analyzed at the Central Laboratory at BAS, M03, M12, at yearly visits thereafter, and as needed. The Central Laboratory will analyze the urine calcium-to-creatinine (instead of the site's clinical laboratory) because: (1) this variable also serves as a safety outcome of interest and would be important to standardize its measurements; (2) the result does not need to be communicated back to the participant urgently. Results will be reported to the clinical site and also provided to participants and their health care provider(s).

- Urine calcium-creatinine ratio

To monitor safety, the following laboratory test will be drawn and analyzed at each *site's clinical laboratory.*

- Pregnancy test for women of reproductive potential who report missing two consecutive menstrual periods *based on the participant's typical menstrual cycle*.

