10.1.1 Potential risks related to this study

The potential risks that may be seen in this study are shown below.

“Expected” AE related to the *intervention, vitamin D supplementation* (uncommon).

- Hypercalcemia
- Hyperphosphatemia
- Nephrolithiasis
- Hypercalciuria
- Nephrotoxicity
- Anemia
- Polyuria
- Nausea
- Vomiting
- Poor appetite
- Weakness
- Fatigue
- Insomnia
- Headache
- Metallic taste

“Expected” AE related to *study procedures for outcome assessment (testing)*

Related to blood draws

- Minor discomfort from introducing the needle/catheter under the skin or skin bruise (common)
- A skin infection from the needle/catheter (rare)
- Mild anemia from repeated blood draws (rare)
- Nausea, vomiting and syncope (uncommon)

Related to the OGTT

- Risks associated with insertion of needle/catheter and mild anemia as described above
- Phlebitis (rare)
- Symptoms or signs of hypoglycemia following the oral glucose load (uncommon)
- Nausea, vomiting

Other risks related to overall trial participation

- Social-psychological risk due to inadvertent disclosure of confidential medical information (rare)

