During the study, to minimize the occurrence of “expected” AE and overall risk, the following measures will be taken:

Intervention

- Serum calcium and creatinine (GFR), and urine calcium excretion will be monitored at regular intervals.
- At each contact (phone or visit), participants will be questioned in regards to changes in their health or medications (prescription or non-prescription, including supplements).

Outcome Measures

- For all blood draws/catheter insertion, research staff will follow the usual sterile techniques and only experienced personnel will perform the procedure to minimize discomfort, bruising and risk of infection or bruising.
- To minimize the risk of anemia from repeated blood draws, the smallest amount of blood required for each testing procedure will be drawn.

Trial Participation

- A site study physician (or his designee) will be available at all times to evaluate and provide the necessary medical intervention in the event of an adverse event, or make a referral for the appropriate care.
- Risk to patient confidentiality is minimal because all study records are confidential within the study staff environment. Although the consent form will specify what protected health information will be collected and with whom it will be shared, an authorization form in addition to the consent form will be signed by participants from institutions that require a separate document in accordance with their interpretation of the Health Insurance Portability and Accountability Act (HIPAA) guidelines. Safety precautions and encryption of data will ensure that electronic systems do not pose a risk to participant confidentiality. Study results will be published, but participant identity will not be revealed in any articles or scientific presentations and records will be kept as required by federal and state laws and regulations.

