3.4 Safety outcomes: binary variables

- Hypercalcemia, as defined in the protocol and Data Safety and Monitoring Plan
- Hypercalciuria, as defined in the protocol and Data Safety and Monitoring Plan
- Nephrolithiasis, as reported by clinical sites and Data Safety and Monitoring Plan

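### Kidney dysfunction permanently stops study pills under the protocol, but it is the one such condition that the SAP does not list for comparison between arms

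*SAP*

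**What the plan says.** Protocol 7.5 states that "study pills will be permanently discontinued for: hypercalcemia, nephrolithiasis, hypercalciuria and kidney dysfunction", by criteria set out in the DSMP.

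SAP 3.4 defines three binary safety outcomes: hypercalcemia, hypercalciuria and, last in the list, "Nephrolithiasis, as reported by clinical sites and Data Safety and Monitoring Plan". SAP section 6 says "The safety analyses will examine the effect of vitamin D supplementation on the following safety outcomes" and repeats the same three. It names no statistical method and no analysis set for any of them.

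Elsewhere the protocol treats kidney function as a safety matter:

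- Section 3.1 gives the objectives as "to evaluate the safety of oral daily vitamin D supplementation and its effect on the time to onset of clinical diabetes". Safety and tolerability is also a secondary aim (3.2.2) and a secondary outcome (9.2).
- Section 10.1.1 lists "Nephrotoxicity" among the expected adverse events of the intervention.
- Section 10.1.2 says that "Serum calcium and creatinine (GFR), and urine calcium excretion will be monitored at regular intervals". Section 8.2.2 sets the times as M03, M12 and yearly, and the Schedule of Procedures adds screening.
- Section 5.2 explains that the entry GFR cutoff was chosen to "ensure that participants maintain GFR > 40 mL/min during the study".

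**The concern.** An SAP that enumerates its safety outcomes fixes what the final safety analysis must contain. Here the list stops one short of the conditions that the protocol considers serious enough to end treatment for good. The omitted one is measured on the same scheduled draws as serum calcium, and serum calcium does reach the SAP, as hypercalcemia.

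If kidney dysfunction, or a fall in GFR, were more common on vitamin D, nothing in the SAP would require the final analysis to show it. A renal comparison decided on after unmasking would have no basis in the SAP and would carry less weight, whichever way it pointed. The trial's safety conclusion is meant to inform long-term supplementation in a large population, so the gap is worth closing.

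**Working it through.** **Step 1: set the lists side by side.**

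| Condition | Stops pills permanently (Protocol 7.5) | Safety outcome (SAP 3.4) | Analysed (SAP 6) |
|---|---|---|---|
| Hypercalcemia | yes | yes | yes |
| Hypercalciuria | yes | yes | yes |
| Nephrolithiasis | yes | yes | yes |
| Kidney dysfunction | yes | no | no |

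Four conditions stand in the first column and three in each of the others. Kidney dysfunction is the only difference, and the SAP lists nothing that 7.5 lacks.

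**Step 2: look for the comparison elsewhere.** Protocol 11.2 covers the primary outcome, subgroups, missing data, interim monitoring and seasonality. It contains no between-arm safety analysis. SAP section 5 compares continuous secondary outcomes in a linear mixed model, but neither creatinine nor GFR is among them. The nearest variable is urine albumin excretion (SAP 3.2.2 and 5.2). It is there as a cardiovascular risk factor in a sub-cohort at baseline, M12 and M24, and is neither GFR nor the stopping criterion. The SAP also has no table of pill discontinuations by arm.

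**Step 3: check that the data would support a comparison.** Participants who stop pills stay in follow-up (7.5). Serum creatinine is still collected after a diabetes diagnosis (8.2.3). Permanent pill discontinuation is recorded as an action taken for adverse events (10.2.1). Three limits apply:

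- Creatinine is drawn at screening, not at the baseline visit (Schedule of Procedures).
- It is measured in each site's own laboratory; only the GFR calculation is central (8.2.2).
- An end-of-study visit that falls on a semi-annual visit has no scheduled creatinine (8.2.3).

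**Step 4: what the comparison could show.** The documents give no rate of kidney dysfunction, so the placebo risks p0 below are assumptions. The sample size is 2,382 randomized 1:1 (Protocol 11.1), so n = 2,382 / 2 = 1,191 per arm. The test is two-sided at 0.05, with no allowance for dropout. With p1 the vitamin D risk and p̄ the mean of p0 and p1:

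Power = Φ{ [ |p1 − p0| − 1.96 √(2 p̄(1 − p̄)/n) ] / √( [p0(1 − p0) + p1(1 − p1)]/n ) }

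For p0 = 1% and p1 = 2%, the null standard error is √(2 × 0.015 × 0.985 / 1,191) = 0.00498 and the alternative standard error is √((0.0099 + 0.0196) / 1,191) = 0.00498. Power is Φ[(0.0100 − 0.00976) / 0.00498] = Φ(0.05) = 52%.

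| Assumed placebo risk | Power, 1.5-fold risk | Power, doubled risk | Vitamin D risk detectable with 80% power |
|---|---|---|---|
| 0.5% | 12% | 29% | 1.7% |
| 1% | 19% | 52% | 2.5% |
| 2% | 35% | 82% | 3.9% |
| 5% | 71% | over 99% | 7.8% |

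For GFR as a continuous measure at one time point, the difference detectable with 80% power is (1.96 + 0.84) × √(2/n) standard deviations. That is 0.11 SD with 1,191 per arm. With the 15% maximum attrition in the synopsis, n is about 1,012 and the figure is 0.12 SD. The documents give no SD, so this is not converted to mL/min.

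**The case against.** The strongest reply is that 7.5 is a rule for managing participants, not a list of endpoints, so the SAP need not mirror it. The protocol does handle GFR somewhat differently. In 5.2 the exclusions for hypercalcemia, hypercalciuria and past nephrolithiasis are tagged as safety, whereas the GFR exclusion is explained by changes in vitamin D homeostasis. Nephrotoxicity is one of 15 expected adverse events, most of which the SAP does not compare. Section 8.2.2 sends urine calcium-creatinine to the Central Laboratory partly because it is a safety outcome of interest, and says nothing of the kind about creatinine. All this is fair, and it shows that the choice of outcomes involves judgment. But kidney dysfunction alone is at once a permanent stopping condition, covered by an expected adverse event and by scheduled safety tests, and absent from the SAP. Local measurement does not set it apart either, since serum calcium is also measured locally.

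A second reply is that the data will be seen anyway. Under 10.3 the DSMB reviews serious adverse events, unanticipated problems and outcome measures, with a summary of non-serious events. The DSMP and the DSMB charter are not among the documents and may call for renal tables by arm. A reader might infer that kidney function will never be compared; the documents do not support that. They show only that neither the protocol nor the SAP plans the comparison. Monitoring during the trial is still not a planned final analysis.

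Third, a reader might take permanent pill discontinuation to be the plan's own measure of tolerability. No passage says so. Pills are also stopped at the participant's request or for other reasons, so a table limited to the four conditions in 7.5 would be incomplete.

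Fourth, a reader might say that ample precision is going unused. For the binary outcome this depends wholly on assumed rates, and at low rates power is poor.

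**Conclusion.** The gap is real and modest. SAP 3.4 and 6 cover three of the four conditions that permanently stop study pills, and no between-arm comparison of the fourth is planned in the protocol or SAP. It goes beyond missing detail because section 6 is an enumerated list which, followed as written, leaves one stopping condition out of the safety analysis.

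The conclusion rests on the list comparison, not on the power figures, which use assumed placebo risks and ignore dropout. Those figures do show how to read the result. The binary outcome could miss a doubling if placebo risk is 1% or less, so its absence from a table of significant differences would not establish renal safety. GFR over time is the more sensitive support, subject to its screening reference value and local assays. SAP section 1 says that some analyses of questionable value were removed. A reader might infer that renal safety was deliberately dropped, but the text does not say which analyses these were.

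**What to change.** In SAP 3.4 and SAP 6:

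1. Add kidney dysfunction, as defined in the DSMP, as a fourth binary safety outcome compared by arm. State the analysis set and method for all four, since section 6 gives none.
2. As support, compare GFR by arm over M03, M12 and the annual visits in the linear mixed model of SAP section 5. Use the screening value as the reference, and note that creatinine is measured in local laboratories.
3. Tabulate permanent discontinuation of study pills by arm for all recorded reasons, not only the four in 7.5.

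The cost is SAP wording and a few tables from data already scheduled. No visit, test, participant or alpha is added. The downside is a few more safety comparisons, to be read descriptively, with limited power for the binary outcome if events are rare. No change to the clinical stopping rule is proposed.
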